8.2.7. Concomitant Medication

Concomitant medications will be reviewed at each visit and recorded in the source documents and eCRF.

8.2.8. Allergic Reactions

Before any SC injection or IV infusion, appropriately trained personnel and medications must be available to treat allergic reactions, including anaphylaxis. All participants must be observed carefully for symptoms of an allergic reaction (eg, urticaria, itching, hives). If a mild or moderate allergic reaction is observed, acetaminophen, non-steroidal anti-inflammatory drugs, and/or diphenhydramine may be administered.

In the case of a severe allergic reaction (eg, anaphylaxis), SC aqueous epinephrine, corticosteroids, respiratory assistance, and other proper resuscitative measures may be essential and must be available at the location where the injections or infusions are being administered.

Participants who experience serious adverse reactions related to an injection or infusion should be discontinued from further study intervention administrations.

Participants who experience reactions following an injection or infusion that result in bronchospasm with wheezing and/or dyspnea that requires ventilatory support, or symptomatic hypotension with a decrease in systolic blood pressure >40 mm Hg or blood pressure <90/60 mm Hg will not be permitted to receive additional study intervention.

Participants who experience reactions suggestive of serum sickness-like reactions (resulting in symptoms such as myalgia and/or arthralgia with fever and/or rash that are not representative of signs and symptoms of other recognized clinical syndromes) occurring 1 to 14 days after an injection of study intervention, should be discontinued from further study intervention administrations. Note that these symptoms may be accompanied by other events including pruritus, facial, hand, or lip edema, dysphagia, urticaria, sore throat, and/or headache.

8.2.9. Adverse Events Temporarily Related to Infusion

Any AE that occurs during or within 1 hour after the IV infusion of study intervention will be carefully evaluated. Minor infusion-related AEs may be managed by slowing the rate of the IV infusion and/or treating with antihistamines and/or acetaminophen (paracetamol) as clinically indicated. If an IV infusion of study intervention is stopped because of an AE that, in the opinion of the investigator, is not severe or does not result in a SAE, the infusion may be restarted with caution.

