6. STUDY INTERVENTION

6.1. Study Interventions Administered

All participants will receive 1 IV infusion at Weeks 0, 4, and 8 (either active or placebo).

All participants will receive 2 SC injections at each visit (either active, active and placebo, or placebo) every 4 weeks from Weeks 0 to 36.

Intravenous study intervention should be administered over a period of not less than 1 hour, and not more than 2 hours. The infusion should be completed within 6 hours of preparation.

Since 2 SC injections will be administered at each administration visit, each SC injection should be given at a different location of the body.

Detailed instructions on the administration of IV and SC study intervention will be provided in the Site Investigational Product (IP) Binder.

Study intervention administration must be captured in the source documents and the electronic case report form (eCRF).

Guselkumab and placebo will be manufactured and provided under the responsibility of the sponsor. Refer to the IB for a list of excipients.

For details on rescue medications, refer to Section 6.5.1. For a definition of study intervention overdose, refer to Section 8.4, Treatment of Overdose.

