7.1. Discontinuation of Study Intervention

A participant's study intervention must be discontinued if any of the following occur:

- The investigator believes that for safety reasons or tolerability reasons (eg, AE) it is in the best interest of the participant to discontinue study intervention.
- The participant has a serious adverse reaction that is temporally related to an injection or an infusion including an injection-site or infusion reaction, resulting in bronchospasm with wheezing and/or dyspnea that requires ventilatory support OR that results in symptomatic hypotension with a decrease in systolic blood pressure >40 mm Hg or blood pressure <90/60 mm Hg. This may include events of National Cancer Institute Common Terminology Criteria for Adverse Events (NCI-CTCAE) toxicity grade ≥3. In general, discontinuation of study intervention administration must be considered for participants who develop a severe injection-site or infusion reaction.
- The participant or their legally acceptable representative withdraws consent/assent for administration of study intervention.
- The participant becomes pregnant or plans a pregnancy during the study period. Refer to Appendix 7 (Section 10.7), Contraceptive and Barrier Guidance and Collection of Pregnancy Information.
- The initiation of protocol-prohibited medications, treatments, or interventions (outlined in Section 6.5, Concomitant Therapy) that have an impact on HS efficacy evaluations.
- The participant has a malignancy including squamous cell skin cancer. Consideration may be given to allow participants, who develop ≤2 basal cell skin cancers and who are adequately treated with no evidence of residual disease, to continue to receive study intervention.
- A systemic opportunistic infection.
- A recurrent or chronic serious infection.
- The participant is deemed ineligible according to the following TB screening criteria:
 - A diagnosis of active TB is made.
 - A participant has symptoms suggestive of active TB based on follow-up assessment questions and/or physical examination or has had recent close contact with a person with active TB and cannot or will not undergo additional evaluation.

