8.2.2. Vital Signs

Vital signs (including temperature, pulse/heart rate, respiratory rate, and blood pressure) will be obtained before and approximately every 30 minutes during every IV infusion, and at approximately 30 minutes after completion of the final IV infusion.

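### Section 8.2.9 lets a stopped infusion be restarted with no exception for the stop rules in 8.2.8 and 7.1, which conflicts with 8.2.8 for threshold hypotension if that section covers mid-infusion reactions

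*Protocol*

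**What the plan says.** Four parts of the protocol bear on a reaction during an infusion.

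- **Section 8.2.9** sets its window first: "Any AE that occurs during or within 1 hour after the IV infusion of study intervention will be carefully evaluated". It then allows a stopped infusion to resume if the event, "in the opinion of the investigator, is not severe or does not result in a SAE, the infusion may be restarted with caution". It does not refer to 8.2.8 or 7.1.
- **Section 8.2.8** has two relevant rules. One covers serious reactions: "Participants who experience serious adverse reactions related to an injection or infusion should be discontinued from further study intervention administrations". The next is defined by clinical features, not seriousness. It opens "Participants who experience reactions following an injection or infusion that result in bronchospasm with wheezing and/or dyspnea" (needing ventilatory support) and goes on to say that those with "symptomatic hypotension with a decrease in systolic blood pressure >40 mm Hg or blood pressure <90/60 mm Hg will not be permitted" any additional dosing. It sets no condition on severity or seriousness.
- **Section 7.1** requires discontinuation for anyone who "has a serious adverse reaction that is temporally related to an injection or an infusion including an injection-site or infusion reaction, resulting in bronchospasm" needing ventilatory support, or in hypotension at the same thresholds. Here the features count only within a serious reaction. The same bullet adds that stopping must be considered after a severe injection-site or infusion reaction.
- **Appendix 6 (Section 10.6)** grades severity by distress and loss of function. Blood pressure is not part of the grade.

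On timing, Section 6.1 states: "Intravenous study intervention should be administered over a period of not less than 1 hour, and not more than 2 hours". Section 8.2.2 has vital signs "obtained before and approximately every 30 minutes during every IV infusion".

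**The concern.** The sentence in 8.2.9 decides whether a participant who has just reacted is re-exposed at the same visit. It relies on two judgments, severity and seriousness. It leaves out the objective blood pressure criterion that 8.2.8 sets one section earlier. Whether an event will result in an SAE may not be known when the decision is made, whereas the blood pressure is.

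The stake is participant safety. Section 2.2 describes prior IV experience as single doses in 30 healthy participants, the highest being 987 mg in one person. This trial gives 1200 mg IV three times, although Section 2.3 notes that the same regimen is being evaluated in Crohn's disease. There is also a compliance side: a site that restarts under 8.2.9 could be recorded under the SAP Section 4.5 deviation category for meeting withdrawal criteria without being withdrawn.

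**Working it through.** The plan states no figure on this point, so the check sets the rules side by side.

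**Step 1. The 'or' in 8.2.9.** Read literally, restart is allowed if the event is non-severe or does not result in an SAE. Only an event that is both severe and serious is excluded. On the stricter reading, which requires neither to be present, both conditions must hold.

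**Step 2. Apply each rule to each kind of reaction.** The 8.2.8 column assumes that the section includes reactions during the infusion.

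| Reaction | 8.2.9, literal | 8.2.9, strict | 8.2.8 | 7.1 reaction bullet |
|---|---|---|---|---|
| Non-severe, non-serious, threshold hypotension | restart allowed | restart allowed | no further dosing | stop not triggered |
| Severe, non-serious, no listed feature | restart allowed | not allowed | no stop rule applies | stopping must be considered |
| Serious, non-severe, no listed feature | restart allowed | not allowed | should be discontinued | stop not triggered |
| Severe and serious | not allowed | not allowed | should be discontinued | stopping must be considered; required with a listed feature |

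In the first row the two sections disagree on either reading of 'or'. Resuming the infusion delivers more study intervention, which 8.2.8 forbids. The second and third rows are a problem only on the literal reading.

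**Step 3. Can the first-row case arise?** Severity is graded on distress and function, so symptomatic hypotension at the thresholds can be graded moderate. It can also be found in time. With checks about every 30 minutes, a 60-minute infusion has one reading before its end (at 30 minutes) and a 120-minute infusion has three (at 30, 60 and 90 minutes). The other listed feature, bronchospasm needing ventilatory support, would hardly be judged non-serious, so hypotension is the practical case.

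**Step 4. The word 'following' in 8.2.8.** Restart matters only while an infusion is unfinished, so the first-row conflict needs 8.2.8 to reach mid-infusion reactions.

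- If it does, 8.2.9 and 8.2.8 contradict each other.
- If it covers only reactions after the infusion ends, the contradiction disappears and a gap takes its place. No feature-based stop then applies to a non-serious reaction mid-infusion, yet the same blood pressure shortly after the end bars all later dosing.

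The broader reading fits better with 8.2.9 and Section 9.4.3, which treat the infusion and the hour after it as one window. The text of 8.2.8 does not settle it.

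**Step 5. Occasions on which the rule could be used.** Randomization of 180 participants 1:1:1 gives 180/3 = 60 per arm. Active infusions number 60 × 3 = 180. Placebo infusions number 120 × 3 = 360. The total is 180 + 360 = 540, and because sites are blinded the rule applies to all of them. This counts infusions, not conflict cases. The documents give no reaction rate from which cases could be estimated.

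**The case against.** The strongest reply is that both rules can be followed. Section 8.2.9 is general and permissive, while 8.2.8 is specific and mandatory and stands immediately before it. Not restarting satisfies both. This is right as far as it goes, but neither document says which section prevails. The detailed IV instructions are in the Site IP Binder (Section 6.1), which is not among the documents reviewed and might say more.

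A second reply is that the case is nearly empty. Section 7.1 lists the same thresholds as features of a serious reaction, and Appendix 6 says events that may jeopardize the participant should usually be considered serious. A site that classed the event as serious would stop under 7.1. This narrows the case but does not remove it: 8.2.8 gives serious reactions their own sentence, so its blood pressure rule does not depend on seriousness.

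Third, the protocol has other protections: the investigator's best-interest stop in 7.1 and independent DMC review of unblinded safety data (Section 9.6). The first uses the same judgment that 8.2.9 relies on, and the second comes after the event.

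A reader might also infer more than the documents support:

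- **That 8.2.8 bars dosing after any symptomatic hypotension.** It does so only at the stated thresholds. Below them there is no conflict with that rule.
- **That the contradiction is certain.** It depends on how 'following' is read (Step 4).
- **That the primary result is at risk.** A participant stopped at Week 0 is followed to about Week 12 (Section 7.1), before the Week 16 assessment, and may count as a nonresponder (Section 9.4.2.1). That is at most 1/60 = 1.7 percentage points in an arm per participant. This effect comes from stopping, which 8.2.8 already requires on the broader reading. It does not measure harm from the restart sentence.

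**Conclusion.** The concern holds as a narrow participant-safety inconsistency, at medium confidence. Section 8.2.9 carries no exception for 8.2.8 or 7.1. It conflicts with 8.2.8 for non-severe, non-serious symptomatic hypotension with a systolic fall above 40 mm Hg or a pressure below 90/60 mm Hg, provided 8.2.8 is read to include reactions during the infusion. Independently of that proviso, the literal 'or' allows restart after a serious, non-severe reaction, against the serious-reaction sentence in 8.2.8. It also allows restart after a severe, non-serious one, which sits badly with the 7.1 instruction to consider stopping. The 'or' is probably a drafting slip. The effect on trial results is negligible, and sample size, power and type I error are untouched. The sentence still merits correction because it governs immediate re-exposure and the correction is cheap.

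**What to change.** Reword the restart sentence in 8.2.9 along these lines: a stopped infusion may be resumed, cautiously, only if the investigator judges that the adverse event is not severe **and** has not resulted in an SAE, and it meets no discontinuation criterion in Section 7.1 or 8.2.8, including symptomatic hypotension at the 8.2.8 thresholds arising during the infusion.

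The final clause settles the restart question however 8.2.8 is read. The change needs no new procedure or data. Its small downside is that a severe, non-serious reaction could no longer be followed by a same-day restart; later dosing would remain a matter of judgment under 7.1.

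Two further edits are optional and belong to the sponsor's clinical judgment: stating in 8.2.8 that it covers reactions during as well as after an infusion, and removing the seriousness condition from the feature rule in 7.1. Both alter permanent stopping rules. If 8.2.8 was meant to apply only after the infusion ends, the first would add discontinuations. Neither is needed to repair 8.2.9.

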8.2.10. Injection-site Reactions

A study intervention injection-site reaction is any adverse reaction at an SC study intervention injection-site. The injection sites will be evaluated for reactions and any injection-site reactions will be recorded as an AE.

8.2.11. Tuberculosis Evaluation(s)

8.2.11.1. Initial Tuberculosis Evaluation

Participants must undergo testing for TB (refer to laboratory manual for QuantiFERON®-TB test or Appendix 4 [Section 10.4] for tuberculin skin test) and their medical history assessment must include specific questions about a history of TB or known occupational or other personal exposure to individuals with active TB. The participant should be asked about past testing for TB, including chest radiograph results and responses to tuberculin skin or other TB testing. Investigators have the option to use both the QuantiFERON®-TB test and the tuberculin skin test to screen for latent TB if they believe, based on their judgment, that the use of both tests is clinically indicated in order to evaluate a participant who has high risk of having latent TB. If either the QuantiFERON®-TB test or the tuberculin skin test is positive, the participant is considered to have latent TB infection for the purposes of eligibility for this study.

Participants with a negative QuantiFERON®-TB test result (and a negative tuberculin skin test result in countries in which the QuantiFERON®-TB test is not approved/registered or the tuberculin skin test is mandated by local health authorities) are eligible to continue with prerandomization procedures. Participants with a newly identified positive QuantiFERON®-TB (or tuberculin skin) test result must undergo an evaluation to rule out active TB and initiate appropriate treatment for latent TB. Appropriate treatment for latent TB is defined according to local country guidelines for immunocompromised patients. If no local country guidelines for immunocompromised patients exist, US guidelines must be followed, or the participant will be excluded from the study.

8.2.11.2. Ongoing Tuberculosis Evaluation

Early Detection of Active Tuberculosis

To aid in the early detection of TB reactivation or new TB infection during study participation, participants must be evaluated for signs and symptoms of active TB at scheduled visits (refer to the Schedule of Activities in Section 1.3). The following series of questions is suggested for use during the evaluation:

- "Have you had a new cough of >14 days' duration or a change in a chronic cough?"
- "Have you had any of the following symptoms:
 - Persistent fever?
 - Unintentional weight loss?
 - Night sweats?"
- "Have you had close contact with an individual with active TB?" (If there is uncertainty as to whether a contact should be considered "close," a physician specializing in TB should be consulted.)

If the evaluation raises suspicion that a participant may have TB reactivation or new TB infection, an immediate and thorough investigation should be undertaken, including, where possible, consultation with a physician specializing in TB.

Investigators should be aware that TB reactivation in immunocompromised participants may present as disseminated disease or with extrapulmonary features. Participants with evidence of active TB should be referred for appropriate treatment.

Participants who experience close contact with an individual with active TB during the conduct of the study must have a repeat chest radiograph, a repeat QuantiFERON®-TB test, a repeat tuberculin skin test in countries in which the QuantiFERON®-TB test is not approved/registered or the tuberculin skin test is mandated by local health authorities, and, if possible, referral to a physician specializing in TB to determine the participant's risk of developing active TB and whether treatment for latent TB is warranted.

Study intervention administration should be interrupted during the investigation. A positive QuantiFERON®-TB test or tuberculin skin test result should be considered for the detection of latent TB. If the QuantiFERON®-TB test result is indeterminate, the test should be repeated as outlined in the laboratory manual. Participants should be encouraged to return for all subsequent scheduled study visits according to the protocol. Participants who discontinue treatment for latent TB prematurely or who are noncompliant with therapy must immediately discontinue further administration of study intervention and be encouraged to return for all subsequent scheduled study visits according to the Schedule of Activities (Section 1.3).

8.3. Adverse Events and Serious Adverse Events

Timely, accurate, and complete reporting and analysis of safety information from clinical studies are crucial for the protection of participants, investigators, and the sponsor, and are mandated by regulatory agencies worldwide. The sponsor has established Standard Operating Procedures in conformity with regulatory requirements worldwide to ensure appropriate reporting of safety information; all clinical studies conducted by the sponsor or its affiliates will be conducted in accordance with those procedures.

54

Adverse events will be reported by the participant (or, when appropriate, by a caregiver, surrogate, or the participant's legally acceptable representative) for the duration of the study.

Anticipated events will be recorded and reported as described in Appendix 2 (Section 10.2), Anticipated Events.

For further details on AEs and SAEs (Definitions and Classifications; Attribution Definitions; Severity Criteria; Special Reporting Situations; Procedures) as well as product quality complaints (PQCs), refer to Appendix 6 (Section 10.6), Adverse Events: Definitions and Procedures for Recording, Evaluating, Follow-Up, and Reporting.

8.3.1. Time Period and Frequency for Collecting Adverse Event and Serious Adverse Event Information

All Adverse Events

All AEs and special reporting situations, whether serious or non-serious, will be reported from the time a signed and dated ICF is obtained until completion of the participant's last study-related procedure, which may include contact for follow-up of safety. Serious adverse events, including those spontaneously reported to the investigator within 12 weeks after the last dose of study intervention, must be reported using the Serious Adverse Event Form. The sponsor will evaluate any safety information that is spontaneously reported by an investigator beyond the time frame specified in the protocol.

Serious Adverse Events

All SAEs occurring during the study must be reported to the appropriate sponsor contact person by study-site personnel within 24 hours of their knowledge of the event.

Information regarding SAEs will be transmitted to the sponsor using the Serious Adverse Event Form and Safety Report Form of the eCRF, which must be completed and reviewed by a physician from the study-site and transmitted to the sponsor within 24 hours. The initial and follow-up reports of a serious adverse event should be transmitted electronically or by facsimile (fax).

8.3.2. Follow-up of Adverse Events and Serious Adverse Events

Adverse events, including pregnancy, will be followed by the investigator as specified in Appendix 6 (Section 10.6), Adverse Events: Definitions and Procedures for Recording, Evaluating, Follow-up, and Reporting.

8.3.3. Regulatory Reporting Requirements for Serious Adverse Events

The sponsor assumes responsibility for appropriate reporting of AEs to the regulatory authorities. The sponsor will also report to the investigator (and the head of the investigational institute where required) all suspected unexpected serious adverse reactions (SUSARs). The investigator (or sponsor where required) must report SUSARs to the appropriate Independent Ethics

Committee/Institutional Review Board (IEC/IRB) that approved the protocol unless otherwise required and documented by the IEC/IRB. A SUSAR will be reported to regulatory authorities unblinded. Participating investigators and IEC/IRB will receive a blinded SUSAR summary, unless otherwise specified.

